5.2.9 Pathology

Pathology shall report on the following criteria for each sample of breast tissue excised during the surgery (main specimen and shaves). It is particularly important that the pathologist reports the tumor distance(s) to the specimen margin(s) for each specimen excised during surgery. Reporting on tumor distances to final margins alone will not allow for determination of study endpoints.

- Type of resection (e.g. lump or shave)
- Tissue dimensions (LxWxH)
- Tissue Weight (g), if available

LUMICELL CONFIDENTIAL

This document is confidential. Do not disclose or use except as authorized.

- Presence/absence of tumor (Invasive Lobular Carcinoma (ILC), Invasive Ductal Carcinoma (IDC), IDC with Ductal Carcinoma *in situ* (DCIS), DCIS only or any combination of these)
- tumor distance(s) to inked margin(s)
- tumor grade
- tumor size
- Other tissue type(s) present, including:
 - LCIS
 - Atypical ductal hyperplasia
 - Usual ductal hyperplasia
 - Inflammation
 - Fibroadipose only
 - Fibroadenoma
 - Papilloma
 - Dense Fibrous
 - Fibrocystic change
 - Apocrine metaplasia
 - Radial scar lesions
 - Biopsy site changes
 - Adenosis

The final margin assessment for a patient is based on the outermost surface. The pathologist will be blinded to the type of shave (Lumicell-guided or standard of care) when conducting the pathology evaluation.

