- f. Mean and median incremental volume (in cubic centimeters) of tissue removed from therapeutic shaves: For each patient, absolute shave volume will be calculated as length (c) × width (c) × depth (c) for each therapeutic shave with the sum by patient of all therapeutic shaves. Subjects with no therapeutic shaves taken will have a therapeutic shave volume of 0cc.

- g. Mean and median contribution of therapeutic shave volume to total tissue removed.

LUMICELL CONFIDENTIAL

This document is confidential. Do not disclose or use except as authorized.

- h. Average number of SOC and therapeutic shaves taken per subject overall and by type of SOC lumpectomy procedure (i.e., lumpectomy with comprehensive shaves vs. lumpectomy with or without selective shaves).
- i. Number of second surgeries recommended as a result of final positive margins.
- j. Rate of second surgeries as a result of a positive margin status following SOC (control arm) and LUM Imaging procedures (device arm).
- k. Rate of cancer found in second surgeries
- l. Number of second surgeries for each patient
- m. Number of images per subject from the cavity after SOC and first round of therapeutic shaves
- n. Secondary analysis of sensitivity and specificity including imaging before removal of SOC shaves.
- o. Number of device issues and malfunctions and their impact to data capture.
- p. Patient-level sensitivity and specificity
- q. Collect exploratory data on tissue types found in therapeutic shaves.
- r. Collect exploratory data on patient reported outcomes.
- s. Analysis of tissue-level sensitivity and specificity for the SOC procedure based on the outermost SOC resected surface.
- t. Adverse events stratified by severity and relatedness to drug/device.
- u. Serious adverse events stratified by severity and relatedness to drug/device
- v. Adverse events by preferred term (sorted by descending occurrences for each preferred term).
- w. Summary of adverse events, overall and split by expectedness to drug/device.
- x. Comparison of adverse events in subjects that have at least one therapeutic shave versus subjects that have no therapeutic shaves.

4 Statistical methods

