4.3.2 Performance goals

The verification of the sensitivity and specificity co-primary endpoints will be a refutation of the null hypotheses

$$H_{01}^s: sen \leq 40\% \text{ against the alternative } H_{11}^s: sen > 40\%$$

$$H_{02}^s: spec \leq 60\% \text{ against the alternative } H_{12}^s: spec > 60\%$$

where *sen* and *spec* represent the true sensitivity and specificity, respectively. The hypotheses involving sensitivity and specificity will be assessed based on the data collected per-tissue level.

These hypotheses will be tested using a one-sided significance level of 2.5%. To account for within-subject correlation, Generalized Estimating Equations (GEE), with a compound symmetry working correlation structure, will be used to estimate sensitivity and specificity along with an equi-tail 95% two-sided confidence interval (CI). The null hypothesis H_{01}^s is rejected if the lower bound of the confidence interval for sensitivity is larger than the performance goal of 40%. Similarly, the null hypothesis H_{02}^s is rejected if the lower bound of the confidence interval for specificity is larger than the performance goal of 60%.

Performance Goals selection for sensitivity and specificity endpoints

Data from the Phase C Feasibility Study showed pathology margin assessment sensitivity to predict cancer in the cavity of ~40%. However, this pathology assessment is done several days after the surgery and can lead to second surgeries. Because the LUM Imaging System provides the additional benefit of assessing the cavity in real-time, a performance goal for instrument sensitivity > 40% is proposed as the success criterion for this hypothesis-tested endpoint. We expect the sensitivity to be similar to that observed in the Phase C study of 69% [95% CI: 56%-80%].

LUMICELL CONFIDENTIAL

This document is confidential. Do not disclose or use except as authorized.

The Phase C data shows that at the current specificity performance of 70% [95% CI: 68%-73%], an average of 1.1 additional shaves were removed guided by the LUM Imaging system, accounting for ~10% of all the total resected tissue. We selected a performance goal for specificity of > 60% to ensure that similar performance in the pivotal trial is obtained regarding tissue removal. Also, with this lower bound, a Youden Index > 0 will be demonstrated to indicate non-random diagnostic performance.

Sample size for testing sensitivity:

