- e. In the case of a SOC shave taken but no image saved before the shave was removed, the shave will be excluded from analysis but will be included in the estimation of SOC margin.
- f. In the case of a protocol deviation where an SOC shave is taken after use of the LUM Imaging System, the analysis will be as follows:

LUMICELL CONFIDENTIAL

This document is confidential. Do not disclose or use except as authorized.

- i. For per tissue sensitivity and specificity: if there is a Lumicell image for this SOC shave, then the SOC shave will be used as truth standard for that orientation. If there is no Lumicell image, then the SOC shave will not be used for sensitivity and specificity evaluation.
- ii. For margin assessment analysis: for the calculation of the SOC margin status versus the margin status after Lumicell, the margin of that SOC shave will be excluded.
- g. In the case of a patient having bilateral lumpectomy, only the data collected from the side of the breast that was imaged will be included in the device performance evaluation.
- h. In the case of an unknown dimension of a shave, the volume of the shave will be assigned as the average volume of that of all the existing shaves of the corresponding type (SOC or therapeutic shaves).

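### SAP 4.11.3h replaces a shave's whole volume with the type average when one dimension is unknown; imputing only the missing dimension would keep the measured data and reduce error in secondary endpoints f and g

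*SAP*

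**What the plan says.** SAP 3.3, endpoint f, reports "Mean and median incremental volume (in cubic centimeters) of tissue removed from therapeutic shaves". The SAP defines the measure as follows: "absolute shave volume will be calculated as length (c) × width (c) × depth (c) for each therapeutic shave", summed within patient. It adds: "Subjects with no therapeutic shaves taken will have a therapeutic shave volume of 0cc". Endpoint g reports the mean and median contribution of therapeutic shave volume to all tissue removed, so SOC shave volumes presumably enter its denominator.

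For missing size, the only rule is SAP 4.11.3, item h. It applies when a dimension of a shave is unknown, and then "the volume of the shave will be assigned as the average volume of that of all the existing shaves of the corresponding type", the types being SOC and therapeutic. Protocol 15.4.6, on missing data, does not address missing dimensions.

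Protocol 5.2.9 requires pathology to report three dimensions for every specimen and lists "Tissue Weight (g), if available" as well. SAP 4.7 summarises continuous measures by mean, SD and 95% confidence interval. SAP 4.12 presents secondary endpoints by type of SOC shave.

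**The concern.** The trigger is a single unknown dimension, but the remedy replaces the whole volume. Two measured dimensions, and the weight where there is one, carry most of the information on that shave's size. The rule uses none of it, and makes no use of patient or orientation either. For SOC shaves the average also pools selective and comprehensive shaves, although SAP 4.12 presents results by those groups.

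Endpoints f and g measure how much extra tissue guided shaving removes, so they describe the cost side of the device. A rule that overrides recorded measurements there should be avoided if a better one is as easy to apply. Three consequences need checking: whether the assigned volume can contradict the recorded size, whether the reported mean and median move, and whether the intervals are affected by treating imputed volumes as observed.

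**Working it through.** The documents give no shave volume, variance or missing-dimension rate, so there is no planned figure to reproduce. Sizes and missing rates below are assumptions unless a source is named.

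**1. Compatibility with the recorded size.** Implied depth = assigned average ÷ (recorded length × width).
- Average 4 cc, shave 1 × 0.5 cm: 4 ÷ 0.5 = 8 cm.
- Average 4 cc, shave 6 × 4 cm: 4 ÷ 24 = 0.17 cm.
- For averages of 2 to 8 cc, the implied depths are 4 to 16 cm and 0.08 to 0.33 cm.

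**2. Error per imputed shave.** Take independent lognormal dimensions with medians 3.5 × 2.5 × 1.0 cm and CV 30% each.
- Median volume = 8.75 cc. Mean = 8.75 × 1.09^1.5 = 9.96 cc.
- Type average: RMSE = 9.96 × √(1.09³ − 1) = 5.4 cc.
- Known length × width × mean depth: RMSE = 9.96 × √(1.09² × 0.09) = 3.25 cc, about 40% lower.
- With CVs of 35/35/45% the figures are 7.7 and 5.4 cc, 30% lower.

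**3. Effect on patient totals, by simulation (600 runs per setting).** SAP 1.1 gives 406 enrolled, and Protocol 5.2.7 gives 10:1 allocation, so about 406 × 10/11 = 369 are in the device arm; 360 were used. Each has a Poisson number of therapeutic shaves with mean 1.1, the Phase C average in SAP 4.3.2. Assumed: lognormal dimensions with medians 3 × 2 × 0.8 cm, CV 40%, within-patient correlation 0.3, and one randomly chosen dimension missing in the affected shaves. The comparator keeps the two known dimensions and fills the third with its mean. Entries are changes from complete data at 5% / 10% / 20% of shaves affected.

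| Missingness | Mean, rule h | Mean, missing dimension only | Patient-total SD, rule h | Patient-total SD, missing dimension only |
|---|---|---|---|---|
| At random | within 0.1% | within 0.1% | −1.3 / −2.5 / −4.9% | −0.5 / −0.9 / −1.9% |
| More often in small shaves | +1.9 / +4.0 / +9.1% | +0.6 / +1.2 / +2.5% | +0.4 / +1.0 / +2.5% | +0.2 / +0.4 / +0.8% |
| More often in large shaves | −1.8 / −4.0 / −9.2% | −0.6 / −1.2 / −2.6% | −2.9 / −6.0 / −13.6% | −1.1 / −2.2 / −4.9% |

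**4. Median.** Under rule h with random missingness, the median over all patients goes from 4.26 to 4.42, 4.24 to 4.58 and 4.27 to 5.04 cc: +3.8%, +8.0% and +18.0%. Among patients with at least one shave it moves by under 0.5%. The difference comes from the zero rule. With mean 1.1, e^−1.1 = 33% of patients have 0 cc, so the overall median sits at the (0.50 − 0.33)/(1 − 0.33) = 25th percentile of those with a shave, where filling in an average pulls values up. The all-patient median under the comparator was not tabulated.

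**5. Scale for the mean.** With 360 × 1.1 = 396 shaves, 20 of them imputed, and the errors from step 2 taken as independent, the error in mean shave volume is 5.4 × √20 ÷ 396 = 0.06 cc under rule h and 3.25 × √20 ÷ 396 = 0.04 cc under the alternative, on a mean of about 10 cc.

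**The case against.** Pathology must report all three dimensions for each specimen, so missing values should be uncommon, and nothing in the documents says which shaves would lack one. If missingness is random the mean is unbiased. At 5% missing, in every pattern tried, the mean moves by less than 2% and the patient-total SD by less than 3%. This stands, and it limits the point to an improvement.

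The phrase in item h may have been meant for shaves whose size is wholly unrecorded. On that reading the type average is a reasonable last resort, and one clarifying sentence would do. The text does not say so, and its natural reading covers a single missing dimension.

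A reader might infer that the rule certainly makes the intervals too narrow. The figures do not support that: the SD falls under random missingness but rises slightly when small shaves are affected more often. A reader might also infer that small shaves are the ones lacking a dimension, so that tissue removal is overstated. No document supports that direction, and the opposite pattern biases the mean downward by about as much.

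Finally, SAP 4.3.2 cites Phase C tissue removal ("accounting for ~10% of all the total resected tissue") in support of the 60% specificity goal, so a reader might infer that the rule bears on that goal. It does not. Specificity is computed from images and truth-standard results, and no volume criterion exists.

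**Conclusion.** The point holds as a defect of the written rule with a modest and unquantified effect. As worded, item h overrides measured dimensions and any weight, and can assign a volume that the recorded size rules out. Its error per imputed shave is larger than it need be: imputing only the missing dimension lowers the RMSE by 30-40% under the assumed CVs in step 2. It can shift the all-patient median, can bias the mean either way if missingness depends on size, and carries no imputation uncertainty.

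With 5-10% of shaves affected, the mean changes by about 2-4% under size-dependent missingness and not at all under random missingness, where the patient-total SD is about 1-3% too small. These figures rest on assumed shave sizes, CVs, missing rates and a Poisson number of shaves; only the average of 1.1 shaves, the enrolment of 406 and the 10:1 ratio come from the documents. Endpoints f and g are secondary and carry no hypothesis test.

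**What to change.** Reword SAP 4.11.3h as follows.
- State what an unknown dimension means: one, two or all three not recorded.
- Keep every recorded dimension and impute only what is missing, for example by the type-specific mean of that dimension or a simple regression on the recorded ones. Where a weight exists, volume may instead be taken from weight, calibrated on shaves that have both weight and dimensions.
- Use the type average volume only when neither a dimension nor a weight was recorded.
- Report the number of shaves imputed, by type.
- Add one sensitivity analysis for endpoints f and g: complete cases, or a bootstrap or multiple imputation that carries the imputation uncertainty.

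Of these, only the dimension-mean version was simulated above. More elaborate modelling is not needed for descriptive endpoints.

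The cost is SAP wording and minor programming. No new data are collected, since dimensions are already required; weight helps only where a site recorded it. Intervals may become slightly wider.

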4.12 Analysis by additional diagnostic subgroups of interest

Primary and secondary endpoints and associated two-sided 95% confidence intervals will be presented by grouping the subjects to those having the comprehensive shaves, having selective shave or no SOC shaves. The purpose of these analyses is to assess consistency within subgroups. Since the study was not powered to detect differences in subgroups, this aim will be considered exploratory in nature and no formal statistical testing will be performed.

4.13 Exploratory Data Analyses

Patient reported outcome measures (PROMs) will be reported as an exploratory endpoint. Also, the type of tissue found in therapeutic shaves will be reported as an exploratory endpoint.

In this protocol, the definition of positive margins is described in section 3.2.2. In addition, Lumicell will collect margin distance information such that alternative definitions (e.g. DICS on ink) can be tested in an exploratory manner.

As an additional exploratory analysis, the sensitivity and specificity in a per-tissue basis for the outermost surface of the SOC procedure will be calculated with their respective 95% confidence interval. For this analysis, only tissue that has a subsequent therapeutic shave or second surgery will be included in the analysis.

5 References

1. Moran, M.S., et al., *Society of Surgical Oncology-American Society for Radiation Oncology consensus guideline on margins for breast-conserving surgery with whole-breast irradiation in stages I and II invasive breast cancer*. *Int J Radiat Oncol Biol Phys*, 2014. **88**(3): p. 553-64.
2. Morrow, M., et al., *Society of Surgical Oncology-American Society for Radiation Oncology-American Society of Clinical Oncology Consensus Guideline on Margins for Breast-Conserving Surgery With Whole-Breast Irradiation in Ductal Carcinoma In Situ*. *J Clin Oncol*, 2016.
3. Bartelink, H., et al., *Impact of a higher radiation dose on local control and survival in breast-conserving therapy of early breast cancer: 10-year results of the randomized boost versus no boost EORTC 22881-10882 trial*. *J Clin Oncol*, 2007. **25**(22): p. 3259-65.

LUMICELL CONFIDENTIAL

This document is confidential. Do not disclose or use except as authorized.

4. Levey, A.S., et al., *A new equation to estimate glomerular filtration rate*. Ann Intern Med, 2009. **150**(9): p. 604-12.

LUMICELL CONFIDENTIAL

This document is confidential. Do not disclose or use except as authorized.

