5.2.2 Collection of baseline Patient Reported Outcome Measures Data

After the patient has consented to participate and has consented to the collection of Patient Reported Outcome Measures (PROMs) Data, prior to surgery start, each enrolled subject should complete this baseline survey collecting data to support an evaluation of PROMs. Baseline evaluations will be electronically collected using the EDC system at any time after the patient consented to participate in the study and prior to their lumpectomy procedure. If the patient has not yet completed their survey at the time of injection, the study site should facilitate and remind the patient to complete their survey. The patient should not complete the baseline survey after the lumpectomy procedure. The completion of the survey is not a requirement to be enrolled into the study. Alternatives to electronic distribution of the surveys may be implemented.

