5.3.2.1 Patient Reported Outcome Measures (PROMs)

Survey data will be collected directly from the patient via an electronic survey tool. Patients who consent to the collection of PROMs will provide an email address at the time of consent. This email address will be entered into the electronic data capture system, but will be blinded to the Sponsor and Sponsor representatives and only available to database administrators and the clinical site. Surveys will be collected at four time points: (1) baseline (before lumpectomy), (2) standard of care follow-up after lumpectomy, (3) three months post lumpectomy and (4) six months post lumpectomy (\pm 6 weeks). Data to be collected may include information about the patient's breast satisfaction (cosmesis) and the patient's feelings about their breast cancer/breast cancer surgery ("cancer worry"). A validated survey tool developed by Memorial Sloan Kettering and McMaster University called the Breast-Q will be used to collect PROMs. Alternatives to electronic distribution of the surveys may be implemented.

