4.1 Demographics and baseline characteristics

Demographic and baseline characteristic including: age, race and ethnicity, menopausal status, mammographic breast density, palpability, cancer histologic type, tumor size, node positive patients, and tumor receptor status (ER/PR/HER2), and baseline body mass index (BMI) calculated from weight and height will be summarized for the study sample. Statistics for continuous variables will include mean, median, standard deviation (SD), minimum, maximum and sample size for the overall sample and grouped by control and device arms, and two-sided 95% CI of the mean difference between (control and study arms). Binary variables will be described with frequencies and percentages for the overall sample. Demographic and baseline characteristics will be summarized by overall using descriptive statistics for analysis populations.

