4.7 Methods for additional analyses

Secondary outcomes involving proportions will be analyzed using methods for Binomial distributions akin to the ones described above. Continuous measurement will be summarized using means and standard deviation and 95% confidence intervals. The percent of people with a specific AE will be reported in prespecified groups. The percent of subjects with adverse events in subjects that have at least one therapeutic shave will be compared with the percent of subjects with adverse events that have no therapeutic shaves using Fisher's exact test or goodness of fit test.

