4.11 General considerations

All analyses will be performed under Good Clinical Practice (GCP) standards using a prespecified statistical analysis plan (SAP). Analyses will be conducted and tables and listings generated using Statistical Analysis System (SAS®) Version 9.4 or higher. Graphics may be prepared with SAS Version 9.4 or higher; R version 3.6.1 or higher, SigmaPlot 12.3 or higher. Subject level data will be provided as a listing to support tables and figures. Summaries will be provided overall, by SOC surgery type (lumpectomy/selective vs comprehensive), and by site.

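### The planned PROM summary uses neither randomised arm nor baseline score, so it cannot show whether assignment to the LUM procedure changed breast satisfaction

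*SAP*

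**What the plan says.** **Analysis.** SAP 4.13 gives PROMs one sentence: "Patient reported outcome measures (PROMs) will be reported as an exploratory endpoint". Protocol 15.4.5 has the same sentence and adds no method. SAP 3.3 also lists PROMs as secondary endpoint r: "Collect exploratory data on patient reported outcomes". Three general rules can therefore apply:

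- SAP 4.7: "Continuous measurement will be summarized using means and standard deviation and 95% confidence intervals".
- SAP 4.11: "Summaries will be provided overall, by SOC surgery type (lumpectomy/selective vs comprehensive), and by site".
- SAP 4.12: "Primary and secondary endpoints and associated two-sided 95% confidence intervals will be presented by grouping the subjects to those having the comprehensive shaves", with selective shaves or no SOC shaves as the other groups.

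**Collection.** Under Protocol 5.2.2, once a woman has consented to PROM collection and before surgery starts, "each enrolled subject should complete this baseline survey collecting data to support an evaluation of PROMs". Protocol 5.3.2.1 continues: "Surveys will be collected at four time points: (1) baseline (before lumpectomy), (2) standard of care follow-up after lumpectomy", then three and six months after lumpectomy. The instrument is the Breast-Q, and breast satisfaction (cosmesis) is named as something the data may include. Neither section restricts collection by arm. Participation is optional, and a baseline survey should not be completed after the lumpectomy.

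**Arms elsewhere in the SAP.** SAP 4.1 plans a "two-sided 95% CI of the mean difference between (control and study arms"), but for listed demographic and baseline variables, and Breast-Q is not among them. SAP 3.3 item j names the control and device arms for the second-surgery rate.

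**The concern.** In the device arm, tissue may be removed beyond standard of care. The protocol takes excessive resection seriously enough to allow at most two therapeutic shaves per orientation (5.2.8.4 and 5.2.12). Whether women notice a cosmetic cost is a natural question for the Breast-Q data, and the trial has a randomised control group and a pre-surgery score with which to address it.

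A mean and SD for all women, or by site or SOC shave type, does not address it. Breast satisfaction after lumpectomy reflects the lumpectomy itself, the woman's starting point and any further surgery. Only a contrast with women randomised to stop after standard of care isolates what assignment to the LUM procedure added.

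Because the SAP names no score, visit or contrast, any arm comparison made later would be chosen after the data were seen. At stake is the use of survey data that patients have already been asked to give. The co-primary endpoints do not depend on it.

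**Working it through.** The documents give no PROM sample size, effect or power, so there is no plan figure to reproduce. The check has two parts.

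**1. Which rules reach Breast-Q, and what do they use?**

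| SAP section | Reaches post-surgery Breast-Q? | Uses randomised arm? | Uses baseline score? |
|---|---|---|---|
| 4.13 | Yes | No | No |
| 4.7 | Yes, as a continuous measurement | No | No |
| 4.11 | Yes | No | No |
| 4.12 | Yes, as a secondary endpoint | No | No |
| 4.1 | No; at most the pre-surgery survey | Yes | Not applicable |
| 3.3 item j | No; second-surgery rate only | Yes | Not applicable |

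The analysis population is also open. SAP 2 makes the mITT population, meaning patients imaged with the system, primary for efficacy analysis of secondary endpoints. SAP 4.5 says efficacy endpoints are assessed without the control tenth. If PROMs fall under those rules, controls may be left out. If PROMs do not count as efficacy, or if controls count as imaged because cavity initialization (Protocol 5.2.5) precedes the reveal of assignment, controls are pooled with device patients. Neither reading gives a contrast.

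This hardly changes the precision of the planned mean at full response: 1.96/√406 = 0.097 SD with controls and 1.96/√369 = 0.102 SD without. Either way the interval is about ±0.10 SD and says nothing about the arm difference.

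**2. How precise would an arm comparison be?**

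Inputs: 406 enrolled (SAP 1.1) and 10:1 allocation (Protocol 5.2.7).

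- Device: 406 × 10/11 = 369.1. Control: 406/11 = 36.9.
- Unadjusted 95% half-width, in SD units: 1.96 × √(1/n_device + 1/n_control).
- Baseline-adjusted: multiply by √(1 − ρ²), where ρ is the correlation between baseline and follow-up scores. At ρ = 0.5 the factor is 0.866.

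The documents give no response rate, SD or ρ. All are assumed here and shown over a range.

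| Response (both arms) | Device / control | Unadjusted | Adjusted, ρ = 0.5 |
|---|---|---|---|
| 100% | 369.1 / 36.9 | 0.34 | 0.29 |
| 75% | 276.8 / 27.7 | 0.39 | 0.34 |
| 50% | 184.5 / 18.5 | 0.48 | 0.41 |
| 25% | 92.3 / 9.2 | 0.68 | 0.59 |

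First row: √(1/369.1 + 1/36.9) = 0.1726, and 1.96 × 0.1726 = 0.338. Last row: √(1/92.3 + 1/9.2) = 0.345, and 1.96 × 0.345 = 0.677.

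- *Other correlations.* For ρ from 0.3 to 0.7, the adjusted half-width runs from 0.32 down to 0.24 SD at full response, and from 0.46 down to 0.34 SD at 50%.
- *Unequal response.* With 75% of device and 50% of control women responding, it is 0.47 SD unadjusted and 0.41 SD adjusted at ρ = 0.5.
- *Small-sample check.* 3,000 simulated linear-model fits with t-based intervals at ρ = 0.5 gave mean half-widths of 0.294 SD (369/37) and 0.422 SD (184/18), close to the formula.

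**The case against.** The strongest reply is that the trial was not built for this comparison. Protocol 5.2.7 says the control arm is there to mitigate surgeon bias. SAP 1 even describes the study as single-arm. PROMs are optional, separately consented and labelled exploratory, and neither document states a cosmetic objective. Where the SAP wanted arms shown for a post-surgery outcome it named them, in item j, so the silence on PROMs may be deliberate. The SAP also measures resection directly through therapeutic shave volume, its share of total tissue, shaves per subject, and adverse events with and without therapeutic shaves (3.3 f, g, h and x). Finally, with an optional survey the control group could shrink to about nine women at 25% response.

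Much of this stands, and it sets the weight of the point: an inexpensive improvement, not an error. It does not remove the point. Tissue volume is not satisfaction, and grouping adverse events by whether a shave was taken is not a randomised comparison. The surveys are already being collected without restriction by arm.

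Some stronger readings are tempting, but the documents do not support them:

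- *PROMs have no analysis method.* SAP 4.7 supplies a mean, SD and 95% CI. Applied visit by visit, it could place the baseline mean beside the later ones. What is missing is an arm contrast and any stated use of baseline as change or covariate.
- *The planned mean is a known mixture with about 9% controls.* That is the randomised share (37/406), but SAP 2 and 4.5 may drop controls, so the composition of the mean is not established.
- *The SAP never shows a post-surgery outcome by arm, or rules such a comparison out for PROMs.* Item j does the first, and nothing in the SAP does the second.

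**Conclusion.** The point holds as a minor one. As written, the SAP would produce Breast-Q summaries that use neither randomised arm nor baseline score, in a population that may or may not include controls. Such summaries cannot show whether assignment to the LUM procedure changed breast satisfaction.

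An arm comparison is feasible on data already planned, but it is imprecise: adjusted half-widths of 0.29 to 0.59 SD for response between 100% and 25%, if ρ is 0.5. These figures rest on 406 enrolled split exactly 10:1, a common SD and ρ in both arms, and assumed response rates. The documents give no important difference against which to judge the widths. The comparison suits exploratory estimation only, and an interval that includes zero would not show that there is no cosmetic effect.

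A reader should not infer that efficacy or safety conclusions are weakened. None of the three co-primary endpoints and no safety analysis uses PROMs.

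**What to change.** Add to SAP 4.13, conditional on breast satisfaction being collected:

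- Show the Breast-Q breast-satisfaction score by randomised arm at each of the four surveys, with response counts by arm and visit. State that control patients are included, whatever the mITT rule says for efficacy endpoints.
- At follow-up, 3 months and 6 months, estimate the device-minus-control difference with 95% CI from a linear model with the baseline score as covariate.
- Analyse women with both a baseline score and a score at that visit, and report how many are excluded for a missing baseline.
- Keep women who have a re-excision or mastectomy in their randomised arm.
- Describe the result as the effect of assignment to the LUM procedure among survey responders. It is not the effect of the shaves, because some device patients have none taken.
- Keep it exploratory, with no hypothesis test, and state the limited precision.

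The cost is SAP wording and one small model per visit, with no new data, visits or patients. The downside is an interval based on at most about 37 controls. Because response is voluntary, randomisation protects the comparison only in part, and the text should warn against reading a null result as absence of a cosmetic effect.
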